#### 2.1.2.1 Definition of responder/non-responder by ACPR

CCI

CCI

**PCR-corrected ACPR at Day X where X=29 (All Parts) or 43 (Parts B & C exploratory analysis)**

- Note: once a patient is declared as non-responder at a particular visit, s/he will remain a non-responder for the subsequent visit.
- Response status at Day X will be derived using following rules for patients whose response is not declared as non-responder at a previous visit:

CCI

CCI

See [Section 5.4](#) for the various scenarios for derivation of the treatment outcomes.

### 2.1.3 Parasite clearance time (PCT)

PCT is defined as the time (in hours) from the first dose until the first total and continued disappearance of asexual parasite forms which remained at least a further 48 hours. PCT will be calculated based on *P. falciparum* asexual parasite counts.

CCI

### 2.1.5 Tail of Kaplan-Meier (KM) plots

As patients may come to visit earlier or later than the targeted day, the tail of KM plots after the last planned assessment day is not reliable due to small numbers of patients at risk. To account for this, time to event/censoring will be reset CCI

This principle will be used for relevant outputs using KM method.

## 2.2 Analysis sets

The following analysis sets are considered for the study:

CCI

CCI FAS for efficacy analyses and PK analysis set for all PK analyses, unless otherwise indicated.

The number (%) of patients in each analysis set will be summarized. Patients excluded from any analysis set will be listed.

### **Analysis set exclusions based on protocol deviations**

Patients may be excluded from the analysis sets defined above based on protocol deviations entered in the database defined in [Table 2-1 Protocol deviations leading to analysis set exclusion](#).

**Table 2-1 Protocol deviations leading to analysis set exclusion**

### **Withdrawal of Informed Consent**

Any data collected in the clinical database after a patient withdraws informed consent from all further participation in the trial will not be included in the analysis. The date on which a patient withdraws full consent is recorded in the eCRF.

#### **2.2.1 Subgroup of interest**

Key efficacy and safety endpoints may be summarized for subgroups of patients by age group (Part B only: <18 and ≥18 years; Part C only: <6 and ≥6 years), sex, region, and relevant resistance mutations.

### **2.3 Patient disposition, demographics and other baseline characteristics**

#### **2.3.1 Patient disposition**

A summary of all screened patients will be presented. Screened patients include those who completed screening and were randomized (or enrolled for Part A optional arms), who completed screening and were not randomized, and who did not complete screening (with reasons for not completing screening).

The following summaries will be provided (with % based on total number of RAS patients):

- Number (%) of patients who were randomized but not treated along with the primary reason for not being treated (based on Treatment disposition page)
- Number (%) of patients who were treated, number (%) of patients who completed treatment phase, and those who discontinued treatment phase along with the primary reason for treatment discontinuation (based on Treatment disposition page)

Patient disposition data and screened patients not randomized will be listed.

### 2.3.2 Demographics and other baseline characteristics

Demographic and other baseline data including disease characteristics will be listed and summarized for the RAS.

The following demographic variables will be summarized:

- Age and age categories (Part A: 18 to <65, ≥ 65; Part B: 12 to <18, 18 to <65, ≥ 65; Part C: 2 to <6, 6 to <12)
- Sex
- Race
- Ethnicity
- Weight and weight categories (Part A: 40 to <75, ≥75 kg; Part B: 35 to <75, ≥75 kg; Part C: 10 to <15, 15 to <25, 25 to <35, 35 to <55, 55 to <75, ≥75 kg)
- Height
- BMI and BMI categories (<16, 16 to ≤25, >25 kg/m^2); BMI (kg/m^2) = weight [kg] / (height [m]) using height and weight at screening visit

The following disease characteristics at baseline will be summarized:

- Body temperature and categories equivalent to axillary method (<37.5, 37.5 to <38.5, ≥38.5 °C) where axillary temperature = oral/tympanic/rectal - 0.5°C
- *Plasmodium* species: *P. falciparum* asexual forms, *P. falciparum* gametocytes, *P. vivax*, *P. ovale*, *P. malariae*, *P. knowlesi*
- CCI  
[REDACTED]  
[REDACTED]  
[REDACTED]
- Gametocytes counts /μL

Categorical data will be presented as frequencies and percentages. In addition to the categories above for continuous data, the mean, standard deviation (SD), median, minimum, and maximum will be presented along with 25th and 75th percentiles for selected parameters.

Relevant medical histories and current medical conditions at baseline will be summarized by system organ class (SOC) and preferred term (PT).

### 2.3.3 Protocol deviations

Protocol deviations will be summarized.

## **2.4 Treatments (study treatment, rescue medication, concomitant therapies, compliance)**

### **2.4.1 Study treatment / compliance**

CCI

### **2.4.2 Prior, concomitant and post therapies**

Prior medications are defined as drugs taken and stopped prior to first dose of study treatment. Any medication given at least once between the day of first dose of study treatment and the last day of study will be a concomitant medication, including those which were started pre-baseline and continued into the treatment period.

Prior and concomitant medications will be coded according to the latest version of WHO Drug Reference List dictionary which employs ATC.

The following will be summarized separately by ATC grade and preferred drug name: (1) prior medications, (2) concomitant medications, and (3) non-study anti-malarial drugs ([Table 5-6](#)). The Safety set will be used.

## **2.5 Analysis supporting primary objective(s)**

Refer to [Section 2.1](#) regarding data presentation.

### **2.5.1 Primary endpoints**

The primary efficacy endpoint in Part A is PCT as defined in [Section 2.1.3](#). FAS will be used for the analysis.

The primary efficacy endpoint in Parts B & C is PCR-corrected ACPR at Day 29 as defined in [Section 2.1.2](#); principal stratum strategy will be used for the analysis with principal stratum defined as adult or adolescent patients (Part B)/children (Part C) with acute uncomplicated *P. falciparum* malaria who are fully dosed (for new combination treatment) or received at least 80% of treatment (for Coartem) and take concomitant medication with anti-malarial activity prior to Day 29 only in case of rescue therapy for recrudescence.

PCT and PCR-corrected ACPR will be used for the primary estimand analyses in Part A and Parts B & C, respectively.

### 2.5.1.1 Assumptions regarding principal stratum strategy

Note first that compliant means fully dosed (for new combination treatment) or received at least 80% of treatment (for Coartem). While the principal stratum includes patients who are compliant with the assigned treatment, some patients may not have been compliant had they been assigned to the other treatment. Thus the ‘true’ principal stratum (i.e. patients compliant regardless of treatment assigned) may be a proper subset of the observed principal stratum. Given the limited sample size, no sensitivity analyses about deviation from the ‘true’ principal stratum will be conducted, thus the following assumptions have been made:

- The response rate for new combination (e.g., INE963+Cipargamin, KLU156+Cipargamin) is the same for patients who are compliant to both new combination and Coartem as for patients who are compliant to new combination only
- The response rate for Coartem is the same for patients who are compliant to both new combination and Coartem as for patients who are compliant to Coartem only

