9.3 Primary endpoint(s)/estimand(s) analysis

9.3.1 Definition of primary endpoint(s)

The primary efficacy endpoint of the study in Part A is the time to parasite clearance (PCT), as defined as the time (in hours) from the first dose until the first total and continued disappearance of asexual parasite forms which remained at least a further 48 hours. PCT will be calculated based on uncorrected *P. falciparum* asexual parasite counts. The FAS will be used for the analysis.

The primary efficacy endpoint in Part B is the PCR corrected Adequate Clinical and Parasitological Response (ACPR) at Day 29 as defined in [Section 8.3.4](#). The FAS will be used for the analysis.

PCT and PCR corrected ACPR will be used for the primary estimand analyses in Part A and Part B, respectively.

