### **2.5.5 Sensitivity analyses**

In Parts B & C, the observed difference between SoC and new combination and 2-sided 80% confidence intervals (CI) of PCR-corrected ACPR will be constructed using the Wilson uncorrected method along with the 2-sided 95% CI for each treatment group using the Clopper-Pearson method.

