### **2.5.6 Supplementary analyses**

Supplementary analyses are not planned for Parts A, B, or C.

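### The Parts B and C non-inferiority test uses an arm-specific compliant stratum, and the visible SAP plans neither a check of its assumptions nor a full-analysis-set result for PCR-corrected ACPR

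*SAP*

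**What the plan says.** SAP 2.5.1 restricts the primary analysis of Parts B and C to patients "who are fully dosed (for new combination treatment) or received at least 80% of treatment (for Coartem"), who also "take concomitant medication with anti-malarial activity prior to Day 29 only in case of rescue therapy for recrudescence". Both conditions concern events after randomisation, and the dosing condition differs by arm.

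SAP 2.5.1.1 notes that "some patients may not have been compliant had they been assigned to the other treatment", so the observed stratum may be larger than the set of patients who would comply on either arm. It then states: "Given the limited sample size, no sensitivity analyses about deviation from the" true principal stratum will be conducted. In their place are two assumptions, one per arm: patients who would comply on either treatment respond at the same rate as patients who would comply only on the one they received.

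The other relevant places are these:

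- **SAP 2.5.5** plans a sensitivity analysis: "2-sided 80% confidence intervals (CI) of PCR-corrected ACPR will be constructed using the Wilson uncorrected method", together with exact 95% intervals per arm. It names no other population.
- **SAP 2.5.6:** "Supplementary analyses are not planned for Parts A, B, or C".
- **SAP 2.2** gives a default: "FAS for efficacy analyses and PK analysis set for all PK analyses, unless otherwise indicated". Section 2.5.1 does indicate otherwise for this endpoint.
- **SAP 1.2.3** defines an all-patient estimand (treatment policy for non-compliance, composite for non-study anti-malarials), but only for uncorrected ACPR.
- **Protocol 9.3.1:** "The primary efficacy endpoint in Part B is the PCR corrected Adequate Clinical and Parasitological Response (ACPR) at Day 29", followed by a statement that the FAS is used. Protocol 9.3.6 adds FAS Kaplan-Meier estimates of PCR-corrected ACPR, while 9.3.3 names a principal stratum strategy.

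**The concern.** Stratum membership depends on what happens after allocation, so randomisation does not protect the comparison. One arm must complete a single administration. The other may miss part of a six-dose course. The people removed need not be alike, and the plan tests neither assumption that would make the comparison fair.

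The route out of the stratum can be a treatment outcome. Under Protocol 12.3.7, a Cohort B2 combination patient who vomits the replacement dose is given rescue treatment. That is not rescue for recrudescence, so by the SAP 2.5.1 definition the patient leaves the primary comparison. For a regimen meant to cure with one dose, failure to retain it is part of how the regimen performs.

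At stake is a non-inferiority statement that holds among compliant patients but not among all treated patients, with no primary-endpoint table showing the difference. Uncorrected ACPR cannot fill the gap, because it counts new infections as failures.

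**Working it through.** **1. What each place covers.**

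| Place | Endpoint | Population |
|---|---|---|
| SAP 2.5.1 | PCR-corrected ACPR, primary test | principal stratum |
| SAP 2.5.1.1 | same | check of stratum assumptions declined |
| SAP 2.5.5 | same, different interval method | not stated |
| SAP 2.5.6 | none planned | – |
| SAP 1.2.3 | uncorrected ACPR | all patients |
| Protocol 9.3.1, 9.3.6 | PCR-corrected ACPR | FAS |

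No visible SAP row pairs PCR-corrected ACPR with the FAS.

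**2. The two dosing rules.** Protocol Table 12-9 lists six Coartem time points. If compliance is counted by doses, 4/6 = 66.7% fails the 80% rule and 5/6 = 83.3% meets it, so one dose may be missed. The single-dose combination allows no shortfall.

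**3. Reproducing the plan's own figures.** The margin and posterior threshold are redacted, so a rule was back-fitted. Inputs are the beta mixtures in SAP 2.5.2 and 30 patients per arm (Table 3-5). The mixture labels are redacted; the one led by beta(148.1, 3.4) is assumed to be the standard-of-care prior. For x responders among n, component j becomes

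Beta(a_j + x, b_j + n − x), with weight proportional to w_j · B(a_j + x, b_j + n − x) / B(a_j, b_j).

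Success is declared if Pr(p_SoC − p_comb < m | data) ≥ t, and power is the sum over both binomial distributions. With m = 0.20 and t = 0.90, all 16 cells of Table 3-5 are matched within 0.005; the cell at 98% and true difference 0.05 gives 0.946 against the printed 0.95. The fit is not unique. Both candidate combination mixtures match, and a vague beta(0.33, 0.33) prior with t = 0.85 matches within 0.008. This shows consistency; it does not confirm the redacted rule.

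**4. Can two patients change the conclusion?** Take standard of care at 30/30, and 30 combination patients of whom two are excluded and counted as failures in the FAS. With 25 responders, the rate moves from 25/28 = 89.3% to 25/30 = 83.3%.

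| Combination prior | t | 25/28 | 25/30 |
|---|---|---|---|
| led by beta(93.5, 1.0) | 0.90 | 0.972 pass | 0.846 fail |
| led by beta(17.9, 1.1) | 0.90 | 0.954 pass | 0.818 fail |
| vague | 0.85 | 0.938 pass | 0.759 fail |

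Other counts behave differently. With the first prior, 27/28 and 27/30 give 0.999 and 0.981, and both pass. A pass at 24/28 depends on the prior: 0.913 under the first, 0.885 under the second.

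**5. Effect on the probability of success.** Standard of care 98%, combination 93% among compliers (difference 0.05), k of 30 combination patients non-compliant and all counted as failures, none in the Coartem arm. The FAS rate is 0.93 × (1 − k/30).

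| k | FAS rate | FAS success | Compliant-only success (two mixture priors) |
|---|---|---|---|
| 0 | 0.930 | 0.95 | 0.95 |
| 1 | 0.899 | 0.82 | 0.90–0.95 |
| 2 | 0.868 | 0.64 | 0.91–0.96 |
| 3 | 0.837 | 0.45 | 0.89–0.92 |
| 4 | 0.806 | 0.29 | 0.90 |

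This is the unfavourable extreme. Exclusions in the Coartem arm, or cures among incompletely dosed patients, would narrow the gap.

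**The case against.** A reader might infer that the SAP forbids an FAS analysis, or all sensitivity analyses, of PCR-corrected ACPR. It does neither. Section 2.5.1.1 declines only analyses of deviation from the true stratum, and Section 2.5.5 does plan a sensitivity analysis. The limited-sample-size reason is given for not examining cross-arm compliance; it is not offered as a reason to omit the FAS.

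Nor is the absence certain. Parts of SAP 2.5.3, 2.6.2, 2.6.5, Section 4 and Table 5-9 are redacted. The SAP follows protocol version 03 of 20 March 2024, which was not supplied, so its difference from the supplied protocol may reflect an amendment.

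The signal would not be wholly hidden. Intercurrent events are counted on the FAS (SAP 2.5.3), and the uncorrected ACPR estimand keeps every patient and treats non-study anti-malarials as failure. Site staff give the doses (Protocol 6.4), a vomited dose can be replaced, and non-evaluable patients may be replaced (Protocol 5.4.1). Exclusions may therefore be few, and 28 need not be the analysed number. Coartem patients can leave the stratum by the same vomiting route.

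All of this stands. It limits how strongly the absence can be stated and how large the effect is likely to be. It does not supply the missing result: event counts and an endpoint that includes reinfection do not show whether the primary conclusion survives in all treated patients.

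**Conclusion.** The point holds in a limited form. The primary non-inferiority test rests on a stratum formed after randomisation by arm-specific rules, its equal-response assumptions go unchecked, and no visible part of the SAP reports PCR-corrected ACPR on the FAS.

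Two excluded patients out of 30 can be enough to reverse the conclusion: 0.95 to 0.97 falls to 0.82 to 0.85 against an assumed threshold of 0.90. This rests on a back-fitted rule, on unlabelled priors, on both patients being failures in the combination arm, and on a non-complier share that the documents do not give. A reader might take it as a prediction that the result will reverse. The documents do not support that, since many counts pass both ways.

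This is a change the sponsor should make. It does not show that the primary estimand is wrong.

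**What to change.** In SAP 2.5.6, for Parts B and C, replace the statement that none is planned with a supplementary analysis of PCR-corrected ACPR on the FAS, by randomised arm, using the same Bayesian model and criteria.

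- Count as non-response, alike in both arms, any rescue or other non-study anti-malarial use before Day 29 that is not treatment of a PCR-confirmed reinfection. Counting treated reinfections as failures would undo the PCR correction.
- Keep patients with incomplete dosing but no such medication at their observed outcome, in line with the treatment-policy element of SAP 1.2.3.
- Report the result beside the primary one. If the two differ, describe the non-inferiority conclusion as applying to compliant patients only. This governs wording and need not be a second success criterion.
- If such an analysis already exists in redacted text, cross-reference it in 2.5.6.

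The cost is one extra table from data already collected. The downside for the sponsor is that the FAS result may be less favourable.

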### 2.5.2 Statistical hypothesis, model, and method of analysis

For Part A, PCT descriptive statistics (mean, standard deviation, median, quartiles) will be provided and Kaplan-Meier curves will be presented. The median PCT and corresponding 2-sided 90% CI will be reported.

For Parts B & C, the primary endpoint will be calculated at Day 29 by computing the percent of patients with PCR-corrected ACPR at Day 29 where presence of *P. falciparum* asexual forms on Day 8 or later is considered as failure (not ACPR) only if the parasite strain observed was already present at baseline based on PCR genotyping. Refer to [Section 2.1.2](#) and [Section 2.1.2.1](#) for details. Note: the primary endpoint is binary with 2 outcomes (ACPR or not ACPR). Beside recrudescence, a patient’s outcome can be classified as not ACPR due to reasons such as missing PCR genotyping at baseline (i.e. PCR result is undetermined), etc. ([Section 2.5.3](#)).

The primary analysis will test for non-inferiority of the CCI based on the dual efficacy criteria as specified below, using a Bayesian approach. CCI

## Part B

CCI

$$0.68 \times \text{beta}(148.1, 3.4) + 0.12 \times \text{beta}(31.1, 1.5) + 0.20 \times \text{beta}(0.33, 0.33)$$

where Beta (a,b) represents a Beta distribution of which the density function is  $x^{(a-1)}(1-x)^{(b-1)}\Gamma(a+b)/(\Gamma(a)\Gamma(b))$ .

CCI [REDACTED]  
[REDACTED]  
[REDACTED]  
[REDACTED]

$$0.25 \times \text{beta}(17.9, 1.1) + 0.14 \times \text{beta}(25.0, 4.8) + 0.06 \times \text{beta}(15.6, 7.8) \\ + 0.05 \times \text{beta}(2.1, 1.3) + 0.50 \times \text{beta}(0.33, 0.33)$$

CCI [REDACTED]  
[REDACTED]  
[REDACTED]

$$0.41 \times \text{beta}(93.5, 1.0) + 0.28 \times \text{beta}(32.2, 2.0) + 0.06 \times \text{beta}(19.6, 5.2) \\ + 0.05 \times \text{beta}(2.6, 1.5) + 0.2 \times \text{beta}(0.33, 0.33)$$

CCI [REDACTED]  
[REDACTED]  
[REDACTED]  
[REDACTED]  
[REDACTED]  
[REDACTED]  
[REDACTED]  
[REDACTED]

[REDACTED] [REDACTED]  
[REDACTED]  
[REDACTED] [REDACTED]  
[REDACTED]

[REDACTED]  
[REDACTED]  
[REDACTED]  
[REDACTED]

[REDACTED]  
[REDACTED]  
[REDACTED]  
[REDACTED]  
[REDACTED]  
[REDACTED]

[REDACTED]

[REDACTED]

[REDACTED]  
[REDACTED]

CCI

### 2.5.3 Handling of intercurrent events

The primary analysis in Part A will account for the below mentioned intercurrent events using a hypothetical strategy. If a patient receives any rescue anti-malarial medication or receives other concomitant medication with anti-malarial activity for any reasons within the first 7 days and before the parasites are cleared, time-to-event PCT will be set to Day 7 (144 hours).

The primary analysis in Parts B & C will account for the below mentioned intercurrent events using a principal stratum strategy. Data will be handled as follows:

[figure not shown]
CCI

The number and percent of patients with intercurrent events will be provided for each intercurrent event using FAS.

### 2.5.4 Handling of missing values not related to intercurrent event

For handling missing values in the primary analysis in Part A, the following strategies apply:

CCI

In Parts B & C, missing values will be handled as per [Table 5-9](#) (#'s 10a-13).

### **2.5.5 Sensitivity analyses**

In Parts B & C, the observed difference between SoC and new combination and 2-sided 80% confidence intervals (CI) of PCR-corrected ACPR will be constructed using the Wilson uncorrected method along with the 2-sided 95% CI for each treatment group using the Clopper-Pearson method.

### **2.5.6 Supplementary analyses**

Supplementary analyses are not planned for Parts A, B, or C.

## **2.6 Analysis supporting secondary objectives**

### **2.6.1 Secondary endpoints**

The secondary efficacy variable in Part A is PCR-corrected and uncorrected ACPR at Day 29 as defined previously in [Section 2.1.2](#). The secondary efficacy variable in Parts B & C is (1) PCT and (2) PCR uncorrected ACPR at Day 29 as defined previously. The key secondary estimands will be used to analyze PCR-corrected ACPR in Part A and PCT in Parts B & C. The other secondary estimand will be used to analyze uncorrected ACPR in Parts A, B, & C. In addition, pharmacokinetics, safety, and tolerability will also be assessed.

### **2.6.2 Statistical hypothesis, model, and method of analysis**

The secondary analysis for Part A will be the computation of percent of patients with PCR-corrected (using principal stratum) and uncorrected ACPR (using FAS) and 2-sided 95% CI for each treatment group using the Clopper-Pearson method at Day 29. No hypothesis testing will be performed.

CCI

[Redacted text block containing multiple lines of blacked-out content]

CCI

- [REDACTED]
- [REDACTED]
- [REDACTED]

PCR uncorrected failure will be classified into: ETF before Day 4, LCF before Day 8, recrudescence, reinfection, negative PCR, missing PCR, or missing assessment. The classification will be done using FAS.

CCI

### 2.6.3 Handling of intercurrent events

CCI

### 2.6.4 Handling of missing values not related to intercurrent events

The same strategy applicable to the primary endpoint in Part A as described in [Section 2.5.4](#) will be used in Parts B & C for PCT. The same strategy applicable to the primary endpoint in Parts B & C as described in [Section 2.5.4](#) will be used in Part A for PCR-corrected ACPR.

Missing values for uncorrected ACPR in Parts A, B, & C will be handled as per [Table 5-9](#) (#'s 10a-13).

For all other endpoints in [Section 2.6.2](#) (i.e. treatment failure endpoints, PCR uncorrected failure classification at each visit, and incidence rates/time to event of recrudescence and reinfection), missing values will be handled directly as missing.

